#### 6.1.1. Medical Devices

The Allergan-manufactured medical device provided for use in this study is VOLUMA with Lidocaine (copackaged with needles, see Table 6-1). Instructions for medical device use are provided in the IDFU and IB.

All device deficiencies (including malfunctions, use error, and inadequate labeling) shall be documented and reported by the PI/TI throughout the clinical investigation (see Section 8.3.6) and appropriately managed by the sponsor.

For investigational use in this clinical study, VOLUMA with Lidocaine must be injected supraperiosteally following a specified injection technique to obtain optimal correction of temple hollowing and aesthetic improvement with minimal safety concern. Study intervention is limited to the temple area. The 27 G 1/2" or 25 G 1" needles supplied with the investigational product must be used.

The TIs must be experienced in the use and administration of HA implants and be practicing in the field of aesthetic medicine, plastic/cosmetic/reconstructive surgery, or dermatology. Before the study begins, the TIs will receive training in the administration of VOLUMA with Lidocaine according to the technique specified for this study. This injection technique is selected since this is a safe and easy-to-follow method for injection (Breithaupt 2015, Sykes 2015).

Anesthesia (ice, topical anesthesia, or local injectable anesthesia) may be administered per the TI's standard practice but must be limited to the treatment area.

The TIs will use aseptic injection technique, and the following procedures must be used to ensure participant safety.

- Determine up to 3 injection sites and mark.
- Inspect and palpate injection sites to identify the location of any superficial vessels, including the superficial temporal artery, and avoid injecting into any vessels.
- Insert the needle at the marked points at an 85° to 90° angle to the plane of the temple until it reaches the periosteum.
- If resistance is felt before reaching the periosteum, withdraw and re-orient the needle.
- Before injection, attempt to aspirate the needle. If blood is observed, withdraw and re-orient the needle.
- Inject VOLUMA with Lidocaine into the treatment area slowly using gentle, even pressure on the syringe.
- Stop injecting immediately if any resistance is felt or if the participant complains of severe pain.

If a vessel occlusion occurs, stop the injection. Treat in accordance with American Society for Dermatologic Surgery guidelines or the Chinese Society of Aesthetic and Plastic Doctor guidelines, which include hyaluronidase injection (Alam 2008, Breithaupt 2015, Carruthers 2015, Minimally invasive Anti-aging Committee 2015).

The detailed recommended injection technique is provided in the IDFU and IB.

# 6.2. Preparation/Handling/Storage/Accountability

- 1. The PI or designee must confirm appropriate temperature conditions have been maintained during transit and pretreatment storage for all study interventions and ensure any discrepancies are reported and resolved before use of the study intervention.
- 2. Only participants enrolled in the study may receive study intervention, and only the TI may administer study intervention. All study interventions must be stored in a secure, environmentally controlled, and temperature monitored (automated) area in accordance with the labeled storage conditions with access limited to the PI/TI and authorized site staff.
- 3. The PI (or a delegated designee) is responsible for study intervention accountability, reconciliation, and record maintenance (ie, receipt, reconciliation, and final disposition records). Include participant identification number, device serial or lot number, and date of treatment.
- 4. Further guidance and information for the final disposition of unused study intervention are provided in the Study Site Binder.
- 5. Devices that are damaged during shipment or at the site or that malfunction during use (eg, faulty syringe or plunger) must be accounted for and returned. The PI will promptly notify the sponsor's Clinical Research department of any device malfunction. The Clinical Research or Product Support representative will provide instruction for the return of any faulty syringe for evaluation.

#### 6.3. Measures to Minimize Bias: Randomization and Blinding

Prior to initiation of study intervention, each consented participant will be assigned a participant number that will be recorded on the appropriate eCRF. At the time of randomization (ie, at the Randomization/Initial Treatment visit), eligible participants will be randomly assigned at a 2:1 ratio to treatment group or control group. For all treatments, the right side will be treated first. Randomization will be within each study site. All participants will be centrally randomized using an IWRS. Before the study is initiated, the log-in information and directions for the IWRS will be provided to each site.

Study intervention will be injected at the study visits summarized in the SoA (Section 1.3). Instructions for preparing and administering the study intervention are provided in the IDFU and IB.

If participants are withdrawn, they will not be replaced.

The EIs and image analysis technicians will remain blinded to each participant's assigned study intervention throughout the course of the study. The PIs/TIs, study coordinators, and participants will not be blinded to treatment, and they will secure the randomization and other records (eg, records of study interventions and prior study assessments) from potential discovery by the

blinded EI. The TIs will not discuss the randomized treatment assignments with or in the presence of the EIs.

In order to maintain the blind, the EI will not be present during any treatment visits and will not have access to any unblinding information (such as treatment eCRFs or device accountability logs). In addition, participants will be instructed not to discuss whether they have received treatment with the EI. Image analysis technicians will only have access to image files that will not contain any unblinding information (such as randomization status or visit name).

In the event of a Quality Assurance audit, the auditor(s) will be allowed access to unblinded study intervention records at the sites to verify that randomization/dispensing has been done accurately.

The EI must remain blinded throughout the study. If a participant requires immediate medical attention by an unblinded physician, this must be provided by the TI whenever possible. In the event that no unblinded physician is available to provide such treatment, the investigational site or sponsor staff may break the blind so that the EI can provide treatment.

Instructions for preparing the study intervention are provided in the IDFU and IB.

Design bias in this study is reduced through the use of a randomized control group, a blinded EI to assess effectiveness results, and the inclusion of objective measures of temple volume that are determined by a blinded image analysis technician.

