# 9.2. Sample Size Determination

The primary effectiveness measure is the change from baseline on the 5-point ATHS at Month 6. The change can range from -4 to +2. The primary effectiveness variable is the ATHS responder status, which is determined by an improvement of 1 grade or more (ie, a change score of -4 to -1) in both temples.

Under a 2:1 randomization ratio, a total of 90 participants in the treatment group and 45 participants in the control group at the primary timepoint will provide at least 90% power to detect a difference of 30% in the responder rates between the groups. This calculation is based on a 2-sided Fisher's exact test at the 5% level, using responder rates of 65% and 35% for both temples simultaneously for participants in the treatment and control groups, respectively. The assumption of a 65% treatment responder rate is a conservative estimate based on the observed responder rate in previous filler studies for other facial areas. Also, while a 30% difference from control is greater than a minimally important difference, a 35% responder rate is a reasonable upper limit of expectation for the control group, based on validation results of the ATHS and control group responder rates observed in previous filler studies. Furthermore, assuming a dropout rate of 20% after randomization through the Month 6 visit, 168 randomized participants are needed, with 112 participants in the treatment group and 56 participants in the control group (2:1 ratio).

If the underlying true responder rate is 65%, 90 participants in the treatment group results in a binomial likelihood of 86.5% to observe a responder rate of at least 60%.

With up to 9 investigational sites planned, it is recommended that no site randomize more than twice the proportional share of 1 more site =  $2 \times [168/(n+1)]$ . The recommended minimum is 8 participants per site, which will guarantee that each treatment group has at least 2 participants at each site (allowing for mixed randomization blocks of 3 and 6 that incorporate the 2:1 randomization ratio).

The commercial software PASS (2008, Version 8.0.13) was used for the power calculation. The sample size calculation used an inequality test for 2 proportions to demonstrate that the treatment group is superior to the control group.

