#### 9.4.2.2. Main Analytical Approach

The primary effectiveness analysis will be performed on the mITT population. The study intervention will be determined to be clinically effective if the following criterion is met:

• The ATHS responder rate for the treatment group is statistically superior to the responder rate for the control group at Month 6

Two-sided Fisher's exact test with 5% significance level will be used to compare responder rates between treatment and the control group. If the 2-sided p-value is  $\leq 0.05$ , which implies that the responder rate is different for treatment than for the control group, and the point estimate of the responder rate for the treatment group is greater than for the control group, then treatment will be considered clinically effective. In addition, responder rates and 95% CIs will be displayed within and between treatment and control groups.

If there are any mITT participants with missing primary effectiveness endpoint, the following missing-data handling method is planned for the primary analysis.

- Multiple imputation by the fully conditional specification method for ordinal data (via SAS procedure MI with FCS logistic statement) will be done with 5 imputed datasets for participants with missing primary endpoint, using the model below:
- Month 6 ATHS =  $\beta_0 + \beta_1 \times \text{Baseline ATHS} + \beta_2 \times \text{Month 1 ATHS} + \beta_3 \times \text{Month 3 ATHS}$
- Intermittent missing ATHS at Month 1 and Month 3 will be imputed by similar models using ATHS at previous visits as covariates.
- The imputation will be performed by treatment group and by side (left and right).
- After imputation, the changes from baseline will be calculated, from which the responder status will be determined.
- Analyses of individual imputed datasets will be performed by SAS procedure FREQ and then pooled by SAS procedure MIANALYZE to display combined responder rates and 95% CIs within and between treatment and control groups and to generate an associated p-value for the comparison of responder rates between groups.

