#### 9.4.3. Secondary Endpoints

Secondary effectiveness endpoints:

- Responder status based on the EI's assessment of the temple area using GAIS at Month 6 after last treatment for treatment group and after randomization for control group, where a "responder" is a participant with grade "improved" or "much improved" on GAIS.
- Responder status based on the participant's assessment of the temple area using GAIS at Month 6 after last treatment for treatment group and after randomization for control group, where a "responder" is a participant with grade "improved" or "much improved" on GAIS.
- Change from baseline on FACE-Q Satisfaction with Facial Appearance questionnaire at Month 6 after last treatment for treatment group and after randomization for control group.
- Change from baseline on FACE-Q Satisfaction with Temples questionnaire at Month 6 after last treatment for treatment group and after randomization for control group.

The following analysis will be performed for the secondary effectiveness endpoints:

- For the responder status based on the EI's and participant's assessments of GAIS at Month 6, the responder rates with 95% exact CI will be summarized, and p-value for between treatment group comparisons will be based on 2-sided Fisher's exact test using observed data.
- Change from baseline on participant responses on FACE-Q Satisfaction with Facial Appearance and with Temples questionnaires, for the Rasch-transformed score (0-100), will be analyzed using a repeated measures mixed-effects model, and the p-value for the between treatment group comparison will be provided for Month 6.

CONFIDENTIAL JUVÉDERM® VOLUMA® with Lidocaine injectable gel

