#### 8.3.2 Handling of Missing Data for the Primary Effectiveness Endpoint(s)

If there are any mITT participants with missing scores for the primary effectiveness endpoint, the following missing-data handling method is planned.

Step 1: The missing data will be imputed by treatment group and by side of the temple using the FCS method for ordinal data (via SAS procedure MI with FCS logistic statement). Thirty (30) imputed datasets will be generated, using *seed* = 1878701 and *nimpute* = 30 based on the following model:

Month 6 ATHS =  $\beta_0 + \beta_1 \times \text{Baseline ATHS} + \beta_2 \times \text{Month 1 ATHS} + \beta_3 \times \text{Month 3 ATHS}$ 

Step 2: With the FCS logistic statement in the MI procedure, each imputed dataset will have ATHS scores of 0, 1, 2, 3, or 4. After imputation, the changes from baseline will be calculated, from which the responder status in ATHS at Month 6 of CP will be determined. Intermittent missing ATHS at Month 1 and Month 3 will be imputed by similar models using ATHS at previous visits as covariates.

Step 3: Each complete (imputed) dataset obtained from Steps 1 and 2 will be analyzed using SAS procedure FREQ.

Step 4: The pooled results will be obtained using PROC MIANALYZE.

The aggregated responder rates by treatment group and the associated p-value and 95% CI will be presented to assess the difference in the ATHS responder rate at Month 6 of CP between VOLUMA and the no-treatment control. If the 2-sided p-value is  $\leq 0.05$ , then the ATHS responder rate at Month 6 in VOLUMA XC is statistically significantly different from that in the no-treatment control group.

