#### 8.4 Secondary Effectiveness Analyses

There are 4 secondary effectiveness measures, to be recorded at the participant level rather than for each temple. The secondary effectiveness endpoints include:

- Responder status for EI assessment of GAIS (described in Table 6) in the temple area at Month 6 during CP
- Responder status for participant assessment of GAIS in the temple area at Month 6 during CP
- Change from baseline in participant responses to FACE-O Satisfaction with Facial Appearance questionnaire, for the Rasch-transformed score (0 - 100) at Month 6 during CP
- Change from baseline in participant responses to FACE-Q Satisfaction with Temples questionnaire, for the Rasch-transformed score (0 - 100) at Month 6 during CP

A GAIS responder for EI assessment is defined as a participant who shows improvement in the overall aesthetic assessment (Improved or Much Improved on GAIS) based on EI assessment in the temple area at the Month 6 visit.

A GAIS responder for participant assessment is defined as a participant who shows improvement in the overall aesthetic assessment (Improved or Much Improved on GAIS) based on participant assessment in the temple area at the Month 6 visit.

For the responder status based on the EI's and participant's assessments of GAIS at Month 6, the responder rates with 95% exact CI will be summarized, and p-value for

between treatment group comparisons will be based on 2-sided Fisher's exact test using observed data.

Grade	Description
Much Improved	Marked improvement in appearance
Improved	Improvement in appearance, but a touch-up or retreatment is indicated
No Change	The appearance is essentially the same as the original condition
Worse	The appearance is worse than the original condition
Much Worse	The appearance is much worse than the original condition

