#### Table 6.Global Aesthetic Improvement Scale

The other secondary effectiveness measures are the participant responses on the FACE-Q questionnaires: Satisfaction with Facial Appearance and Satisfaction with Temples.

Change from baseline on participant responses on FACE-Q Satisfaction with Facial Appearance and with Temples questionnaires, for the Rasch-transformed score (0-100) will be analyzed using a mixed-effects model for repeated measures, and the nominal p-value for the between treatment group comparison will be provided for Month 6.

For FACE-Q Satisfaction with Facial Appearance questionnaire and FACE-Q Satisfaction with Temples questionnaire, the responses to all the items will be summed and converted to a Rasch-transformed score that ranges from 0 to 100 (higher score indicates increased satisfaction) using the algorithm developed by the FACE-Q scale developers.

For items with missing data (which includes selection of more than 1 response for an item, a response of non-applicable (N/A) or skipping a question), insert the unrounded mean of the completed items into the total sum score. The summed score including the imputation of missing items is rounded to the nearest integer and converted to the Rasch transformed score using the conversion table below. Higher scores reflect a better outcome. The converted score ranges from 0 (worst) to 100 (best). If less than 50% of the questions have been answered, then the overall score will be missing.

The secondary effectiveness endpoints will be analyzed based on mITT population based on the observed data.

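### Randomization is within site, but the two gated GAIS tests and the Fisher test for complete ATHS ignore site: the tests are valid, the efficiency loss is small, and Appendix 6 lists no stratification factor

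*Protocol*

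**What the plan says.** - **Randomization.** Protocol 6.3: "Randomization will be within each study site", centrally through the IWRS. Protocol 9.2 sets a recommended minimum of 8 participants per site, "allowing for mixed randomization blocks of 3 and 6 that incorporate the 2:1 randomization ratio". Permuted blocks within site amount to stratification by site.
- **Appendix 6 (Study Tabular Summary).** This table, intended for registry posting, gives the stratification factor as none.
- **ATHS, nothing missing.** Protocol 9.4.2.2: "Two-sided Fisher's exact test with 5% significance level will be used to compare responder rates between treatment and the control group". Site is not mentioned.
- **ATHS, any Month 6 value missing.** Imputation is by arm and temple side, each dataset goes through PROC FREQ, and MIANALYZE is used to "display combined responder rates and 95% CIs within and between treatment and control groups and to generate an associated p-value". SAP 8.3.2 follows the same route with 30 imputations: "the associated p-value and 95% CI will be presented to assess the difference in the ATHS responder rate". Site enters neither the imputation nor the comparison.
- **GAIS (evaluator and participant).** Protocol 9.4.3: "p-value for between treatment group comparisons will be based on 2-sided Fisher's exact test using observed data". SAP 8.4 agrees: "between treatment group comparisons will be based on 2-sided Fisher's exact test using observed data". Both follow ATHS in the fixed sequence (Protocol 9.4.1, SAP 12.0).
- **FACE-Q.** SAP 8.4 says the change scores "will be analyzed using a mixed-effects model for repeated measures" but lists no covariates, so whether site is used cannot be determined. FACE-Q is outside this point.

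**The concern.** Blocking within site balances the arms at each site. If sites differ in their responder rates, that balance removes site variation from the treatment difference, but a test on the pooled 2×2 table still counts it as noise. The test then becomes more conservative than it need be.

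This bears mainly on the two GAIS tests, which are always Fisher tests on observed data. Failing the evaluator GAIS test also closes the participant GAIS test. For ATHS it matters only if every Month 6 score is present, which is unlikely with 20% dropout planned.

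Separately, a registry entry taken from Appendix 6 would misdescribe the randomization given in Protocol 6.3.

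**Working it through.** **1. The plan's own figure.** Inputs from Protocol 9.2: 90 and 45 evaluable, 65% vs 35%, two-sided Fisher test at 5%. Summing the binomial probabilities of all 91 × 46 outcomes with Fisher p ≤ 0.05 gives power 90.8%, which agrees with the stated minimum of 90%. Actual size at a common 35% is 3.8%.

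**2. The stratified test.** At site h, let x be treated responders, n1 and n2 the arm sizes, N = n1 + n2, and m all responders. Then D = Σ(x − n1·m/N), V = Σ n1·n2·m·(N − m)/[N²(N − 1)], and D²/V is referred to chi-square on 1 df (no continuity correction).

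**3. Assumptions not in the documents.** Normal site effects on the logit scale with SD 0 to 1.0, calibrated to keep the marginal rates. At SD 1.0 and a 35% control rate, the middle 95% of sites run from about 6% to 77%. Four simulations:
- A: 9 equal sites, 90/45 complete, 20,000 trials per cell.
- B: 168 randomized in blocks of 3 and 6, unequal sites, those under 15 merged, 20% missing at random, 6,000 trials per cell; 9 sites of 8–33, or 7 sites of 8–42 (SAP 2.4 plans 7).
- C: 9 sites, blocks of 3 and 6, 20% missing.
- D: as B with 9 sites, 4,000 trials per cell, used only in step 5.

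**4. Power, Fisher vs CMH (%), gap in brackets** (gaps for A from unrounded results).

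| Rates | Run | SD 0 | SD 0.25 | SD 0.5 | SD 1.0 |
|---|---|---|---|---|---|
| 65 vs 35 | A | 90.7 vs 91.5 (0.7) | – | 91.2 vs 92.9 (1.7) | 92.5 vs 95.6 (3.1) |
| 65 vs 35 | B, 9 sites | 90.0 vs 91.2 (1.2) | 90.1 vs 91.5 (1.4) | 91.0 vs 92.7 (1.7) | 91.8 vs 95.1 (3.3) |
| 65 vs 35 | B, 7 sites | 90.2 vs 91.4 (1.2) | 90.7 vs 91.9 (1.2) | 90.2 vs 92.1 (1.9) | 91.1 vs 94.9 (3.8) |
| 65 vs 35 | C | – | – | 90.8 vs 92.6 (1.8) | 90.2 vs 94.6 (4.4) |
| 60 vs 35 | A | 78.0 vs 79.0 (1.0) | – | 78.3 vs 81.3 (2.9) | 79.5 vs 86.1 (6.6) |
| 60 vs 35 | B, 9 sites | 76.0 vs 78.1 (2.1) | 77.2 vs 79.5 (2.3) | 77.4 vs 80.7 (3.3) | 77.9 vs 84.4 (6.5) |
| 60 vs 35 | C | – | – | 77.9 vs 81.7 (3.8) | 77.7 vs 84.7 (7.0) |

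The documents give no GAIS rates; 60% vs 35% is an assumption. At 80% vs 10% both tests have 100% power.

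**5. How much is due to site?** Replacing Fisher by CMH makes two changes: it leaves an exact test and it adds site. Comparing like with like:
- 65% vs 35%, exact stratified test against Fisher (B, 9 sites; SD 0, 0.25, 0.5, 1.0): 89.7 − 90.0 = −0.3; 90.0 − 90.1 = −0.1; 91.2 − 91.0 = +0.2; 94.0 − 91.8 = +2.2.
- 65% vs 35%, CMH against uncorrected chi-square (A): 92.9 − 92.3 = 0.6 at SD 0.5; 95.6 − 93.5 = 2.1 at SD 1.0. Run D gives 93.6 − 90.6 = 3.0 at SD 1.0 (exact stratified against Fisher).
- 60% vs 35%: A gives 1.8 at SD 0.5 and 4.6 at 1.0 (CMH against chi-square). D gives 78.4 − 78.2 = 0.2 and 82.0 − 78.6 = 3.4 (exact stratified against Fisher).

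**6. Size at a common 35%, 9 sites (B; SD 0, 0.25, 0.5, 1.0).** Fisher 4.1, 4.1, 3.7, 3.1%; CMH 5.1, 5.5, 5.1, 5.1% (Monte Carlo SE about 0.3). Over all settings of B, Fisher 2.1–4.1% and CMH 4.2–5.5%.

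**7. Imputed ATHS.** SAP 8.3.2 does not name the statistic pooled, so the planned analysis was taken as the risk difference with Wald standard error, pooled by Rubin's rules over 30 imputations. Against the pooled site-stratified Mantel-Haenszel risk difference, with ordinal by-side imputation, 9 sites and assumed visit and between-temple correlations of 0.7 and 0.5, power is 95.4 vs 95.6, 95.4 vs 95.4, 96.6 vs 96.9 and 96.0 vs 96.7%. The gains are 0.2, 0.0, 0.3 and 0.7 points. Mean CI width at SD 1.0 is 31.8 vs 30.1 points. A simpler binary imputation gives at most 95.5 − 94.4 = 1.1 points.

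**The case against.** The case for leaving the plan alone is strong. Fisher's test is the one the trial was sized on, its power at the design rates does not fall below 90% in any setting examined, and its error rate is below 5%. The documents supply no between-site SD. They report rater agreement above 0.60 for ATHS (Protocol 4.2.4) and recommend the same evaluator for each participant (Protocol 8), so an SD of 1.0 may be unrealistic. The GAIS loss rests on rates chosen for illustration. CMH gives up a conservative exact test for an asymptotic one.

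Most of that stands. It is why the point is minor, and why the primary analysis of imputed ATHS should not change. It does not remove two things: Appendix 6 disagrees with Protocol 6.3, and analysing by the factor used in randomization costs almost nothing.

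A reader might infer more than the documents support:
- **That omitting site invalidates the tests or inflates type I error.** The simulations show the reverse: Fisher becomes more conservative as sites differ.
- **That Appendix 6 means allocation was not stratified by site.** Protocol 6.3 is the operative text; the table entry governs no analysis.
- **That sites are known to differ on effectiveness.** SAP 13.0 records that one site reported all injection site responses as adverse events. That is a safety-reporting practice, not evidence about ATHS or GAIS.

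**Conclusion.** The point holds as a minor one. Randomization is within site; the gated GAIS tests and the complete-data ATHS test do not use it. No stated figure is wrong and the sample size needs no change.

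Against CMH, the loss is about 1 to 2 power points at 65% vs 35% for an SD up to 0.5 and about 3 to 4 at 1.0. At 60% vs 35% it is about 2 to 4 points in the runs with missing data (1.0 to 2.9 in run A) and 6 to 7 at SD 1.0. Site itself adds almost nothing up to SD 0.5 at the design rates, and 2 to 3 points near 1.0. At 60% vs 35% it adds 0.2 to 1.8 points at SD 0.5, where the runs disagree on whether leaving the exact test explains most of the gap, and about 4 (3.4 to 4.6) at 1.0.

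For imputed ATHS, the likely route, the gain is near nil. All sizes rest on the assumed SDs, and for GAIS on assumed rates.

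**What to change.** Before database lock:
1. Use the site-stratified CMH test for the two gated GAIS comparisons, and for ATHS if no Month 6 score is missing. Keep Fisher's exact test as a sensitivity analysis.
2. Prespecify how small sites are merged, since the recommended minimum of 8 guarantees only 2 per arm. The threshold is a choice; merging sites under 15, as an illustration, changed power by at most 0.3 points.
3. If ATHS is imputed, keep the planned multiple-imputation analysis as primary. Add the site-stratified Mantel-Haenszel risk difference, pooled over the 30 datasets, only as a sensitivity analysis.
4. Name site as the stratification factor in Appendix 6.

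The cost is SAP wording, one stratification variable in PROC FREQ and one table entry. The downsides are an asymptotic test (simulated size about 4 to 5.5%, against about 2 to 4% for Fisher) and little gain if sites do not differ. If the database is already locked, Protocol 9 requires the change to be documented in the study report as a deviation from the planned analysis; CMH then belongs there as a sensitivity analysis.
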